### **3.3.4.2 Withdrawal of consent to trial participation**

Subjects may withdraw their consent to trial participation at any time without the need to justify the decision. If a subject wants to withdraw consent, the investigator should be involved in the discussion with the subject and explain the difference between trial treatment discontinuation and withdrawal of consent to trial participation, as well as explain the options for continued follow up after trial treatment discontinuation, please see Section [3.3.4.1](#) above

### **3.3.4.3 Discontinuation of the trial by the sponsor**

Boehringer Ingelheim reserves the right to discontinue the trial at any time for any of the following reasons:

1. Failure to meet expected enrolment goals overall or at a particular trial site
2. New toxicological findings, serious adverse events, or any safety information invalidating the earlier positive benefit-risk assessment. Dose escalation will be terminated if more than 50% of the subjects at one dose level show drug-related and clinically relevant adverse events of moderate or severe intensity, or if at least one drug-related serious adverse event is reported.
3. Violation of GCP, or the CTP, or the contract with BI impairing the appropriate conduct of the trial.
4. The sponsor decides to discontinue the further development of the investigational product
5. Dose escalation will be stopped if at least 2 subjects on active treatment at one dose level have relevant individual QT prolongations, i.e. a QTc increase of greater than 60 ms from baseline in connection with absolute QT or QTc greater than 500 ms, as confirmed by a repeat ECG recording
6. Dose escalation will be stopped, if the  $C_{max}$  or  $AUC_{0-24}$  of at least 1 subject of one dose group increases above the following exposure thresholds or if the estimated gMean exposure is expected to exceed a  $C_{max}$  of [REDACTED] or an  $AUC_{0-24}$  of [REDACTED]. Estimation will be done based on preliminary PK results of preceding dose groups (see Section [7.4](#))
7. Occurrence of severe non-serious adverse events considered as drug-related by the investigator in 2 subjects of the same dose group (8 subjects).

The investigator / trial site will be reimbursed for reasonable expenses incurred in case of trial termination (except if item 3 applies).

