#### 1.2.5 Clinical experience in humans

This is the first-in-human trial with the [REDACTED] BI 1595043 consisting of 7 original dose groups that have been completed. These include dose levels 1 mg, 3 mg, 6 mg, 12 mg, 25 mg, 50 mg, and 90 mg of BI 1595043, administered as oral solution, with 6 subjects in each dose group assigned to active treatment and 2 subjects assigned to placebo. To date, BI 1595043 was administered to 42 healthy male subjects within 7 dose groups, and additional 14 healthy male subjects received matching placebo.

The clinical trial protocol is being amended to add the new maximum dose level of 160 mg of BI 1595043 (see Section 1.3.2).

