#### 1.4.3.6 Risk minimization (safety precautions and stopping rules)

The following risk minimization measures, including safety precautions and stopping rules, **will be implemented in this study**:

- Careful selection of starting dose, as described in Section [1.3.1](#).
- Decreasing escalation factors with increasing doses, as described in Section [1.3.2](#). Dose escalations will only be allowed after documented interim safety reviews (see Section [3.1](#)).
- Preliminary measurement of BI 1595043 pharmacokinetics ( $C_{max}$ ,  $AUC_{0-24}$ ; see Section [7.3.2](#)). The expected exposure in the next higher dose group will be estimated based on preliminary PK data of preceding dose groups. The next higher dose level will only be administered, if estimated mean values of  $C_{max}$  and  $AUC_{0-24}$  do not exceed the maximum acceptable human exposure (see Section [1.3.2](#)).
- For safety reasons, division of each dose group of 8 subjects (6 on active treatment, 2 on placebo) into 3 staggered cohorts. On the first study day of each dose level, 2 subjects (Cohort 1) will be treated (one with active treatment, the other with placebo). On the second study day, the next 2 subjects (Cohort 2) will be treated (two with active treatment). On the third study day of each dose level, the remaining 4 subjects (Cohort 3) will be treated (three with active treatment, one with placebo). If BI 1595043 was safe and well tolerated in Cohort 1, the study will continue with Cohort 2. If it was safe and well tolerated in the preceding cohorts, the study will continue with Cohort 3. Between the first application of BI 1595043 in each cohort, there will be a time interval of at least 24 h which is expected to cover the peak exposure of the compound. In Cohort 2 and Cohort 3, subjects will be dosed at least 10 min apart.

Proprietary confidential information © 2021 Boehringer Ingelheim International GmbH or one or more of its affiliated companies

- A monitoring of safety laboratory with specific focus on plasma glucose levels and liver enzymes (see [Flow Chart](#)).
- An ECG monitoring including continuous ECG measurement over 4 hours post dose to cover the anticipated period of highest drug exposure and additional repeated triplicate 12-lead ECGs up to 48 hours following drug administration. Dose escalation would be stopped as soon as at least 2 subjects at one dose level showed relevant QT prolongation (see Section [3.3.4.3](#)).

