The dose groups to be evaluated are outlined in Table [3.1: 1](#) below.

Table 3.1: 1

Dose groups

Dose Group	1	2	3	4	5	6	7	8
Dose (mg)	1	3	6	12	25	50	90	160
Number of subjects	8	8	8	8	8	8	8	8
Subjects receiving placebo	2	2	2	2	2	2	2	2
Subjects receiving BI 1595043	6	6	6	6	6	6	6	6

The groups will be dosed consecutively in ascending order, and a time interval of at least 7 days will be maintained between the last drug administration to subjects in the previous dose group and the first drug administration to subjects in the subsequent dose group. The decision to treat the next dose group will be based upon safety, tolerability and pharmacokinetic data of all the preceding dose groups. The next dose group will only be treated if, in the opinion of the investigator, no safety concerns have arisen in the preceding dose groups (i.e. no dose-limiting events occurred), and if none of the pre-specified trial-specific stopping criteria have been met (refer to Section [3.3.4.1](#)).

A documented Safety Review must take place prior to each dose escalation. Furthermore, an unscheduled safety review meeting can be requested anytime by the Principal Investigator (or an authorised deputy) or the sponsor of the study (for instance, due to the occurrence of any unforeseen adverse events).

Although no formal Safety Review meeting will take place within a given dose group, safety will be continuously monitored during this trial, and an individual will only be dosed in the absence of any safety concern (i.e. no dose-limiting events occurred) and if none of the pre-specified trial-specific stopping criteria have been met (refer to Section [3.3.4.1](#)).

At minimum, data from 4 subjects on active drug need to be available for escalation to a higher dose. For the minimum dataset with regards to preliminary PK data, see Section [7.4](#). The minimum data set for review consists of the following:

- AEs in the current and preceding dose groups up to at least 48 h post dosing, including clinically relevant findings from ancillary safety testing listed below (Note: AEs may be ongoing at the time of Safety Reviews and AE information may be subject to change prior to Database Lock)
- Results from 12-lead ECG and continuous ECG monitoring in the current and preceding dose groups up to at least 48 h post dosing
- Vital signs in the current and preceding dose groups up to at least 48 h post dosing

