- Clinical laboratory tests in the current and preceding dose groups up to at least 48 h post dosing
- Preliminary PK data for the selected time as per Section [7.4](#). For escalation from dose group 1 to dose group 2, preliminary PK data are not required.
- Check of criteria for stopping subject treatment as per Section [3.3.4.1](#)

Proprietary confidential information © 2021 Boehringer Ingelheim International GmbH or one or more of its affiliated companies

The decision to escalate the dose will be made jointly by the Principal Investigator (or an authorised deputy) and the Clinical Trial Lead (or an authorised deputy) after in-depth analysis of all available safety data, especially SAEs (if occurred), AEs, and out-of-range laboratory results (if considered clinically significant). In addition and depending on the results and findings, suitable experts from the sponsor or external institutions may be consulted on as needed basis. In these cases expert recommendations will be documented in the minutes of the Safety Review and considered for the decision making. Dose escalation will only be permitted if no safety concerns exist neither in the opinion of the Principal Investigator (or an authorised deputy) nor the Clinical Trial Lead (or an authorised deputy).

Safety Reviews can be conducted face-to-face or by video/telephone conference. The Clinical Trial Lead (or an authorised deputy) is responsible for the organisation and minutes of the reviews. Minutes will be signed off by the Principal Investigator (or an authorised deputy) and Clinical Trial Lead (or an authorised deputy), and will be filed in the ISF and TMF.

An overview of all relevant trial activities is provided in the [Flow Chart](#). For visit schedules and details of trial procedures at selected visits, refer to Sections [6.1](#) and [6.2](#), respectively.

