#### **4.1.5 Blinding and procedures for unblinding**

##### **4.1.5.1 Blinding**

The trial is designed single-blind. The treatments administered (active or placebo) will be blinded to subjects, but will be known to the investigators (outcome assessors). Only the current dose level will be known to the subjects due to the rising dose design.

A single-blind design is considered acceptable because the potential bias in this type of study seems to be low and according to study procedures it is assured that the investigator's knowledge of the next treatment does not influence the decision to enter a subject.

All trial data will be handled open label. This means that trial functions of the sponsor are unblinded (including clinical trial lead, data manager, statistician, bioanalyst, pharmacokineticist, pharmacometrist, drug metabolism scientist as well as dedicated personnel of the trial site).

Within the central ECG lab, the staff involved with interval measurements will be blinded with respect to the treatment and also with regard to the recording date and time as well as planned time points of the ECGs. The interval measurements for a given subject will be performed in a random and blinded sequence by a single technician. No more than two different blinded readers will evaluate the ECGs of the study.

If a preliminary analysis of ECG data is required during the trial, a part of the staff of the central ECG lab (different from the ECG evaluation team) may be unblinded. This part of the staff will receive the necessary information, which will be stored with no access to the ECG evaluation team.

Access to the randomisation schedule will be controlled and documented by a signed confidentiality statement, which will be stored in the TMF.

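### Does the more-than-50% adverse-event stop need to say whether placebo subjects count?

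*Protocol*

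**What the plan says.** Section 3.3.4.3 of the protocol lists the grounds on which the sponsor may end the trial or stop escalation. Three items count subjects with safety findings, each on its own basis:

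- Item 2, the rule at issue: "Dose escalation will be terminated if more than 50% of the subjects at one dose level show drug-related and clinically relevant adverse events", restricted to moderate or severe intensity. The same item also stops escalation for a single drug-related serious event.
- Item 5 names the active arm: "Dose escalation will be stopped if at least 2 subjects on active treatment at one dose level have relevant individual QT prolongations".
- Item 7, on severe non-serious events, names the whole group: "considered as drug-related by the investigator in 2 subjects of the same dose group (8 subjects".

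Section 1.4.3.6 describes the "division of each dose group of 8 subjects (6 on active treatment, 2 on placebo) into 3 staggered cohorts". On the data needed before a step up, Section 3.1 says: "At minimum, data from 4 subjects on active drug need to be available for escalation to a higher dose". It then leaves the decision to two people jointly: "Dose escalation will only be permitted if no safety concerns exist neither in the opinion of the Principal Investigator", and the same is required of the Clinical Trial Lead. Under Section 4.1.5.1 the allocation is hidden from subjects "but will be known to the investigators (outcome assessors".

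**The concern.** Item 2 is a mandatory rule expressed as a percentage, with no count and no arm. Its neighbours state their basis, so the silence is noticeable. Usage elsewhere does not settle it: Section 1.4.3.6 paraphrases the active-only QT rule without mentioning active treatment, yet also counts a placebo subject as part of a dose level.

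Because investigators know who received placebo, they may judge no placebo event drug-related. The all-subjects reading would then require 5 of the 6 active subjects (83%), against 4 of 6 (67%) on the active-only reading. A review on the permitted minimum of 4 active subjects adds a further question: planned, dosed or with-data subjects. Two people applying item 2 to the same data could disagree on whether escalation must stop. Item 2 is also the only numerical adverse-event rule for a cluster of moderate, non-serious, drug-related events.

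**Working it through.** **Inputs.** Each group has 6 active + 2 placebo = 8 subjects, and 8 groups × 8 = 64 (Section 3.1 and Table 3.1: 1), matching Section 7.7. By cohort, active subjects are 1 + 2 + 3 = 6 and placebo subjects 1 + 0 + 1 = 2. The threshold is strictly above 50%. The plan states no triggering count, so there is none to reproduce.

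**Trigger.** The smallest whole number above half of n is floor(n/2) + 1.

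- n = 8: 5 subjects (62.5% of 8).
- n = 6: 4 subjects (66.7% of 6).

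**Where the readings part.** Let a be qualifying active subjects and b qualifying placebo subjects. All-subjects fires when a + b ≥ 5; active-only fires when a ≥ 4. In a full group they disagree in two patterns: a = 4, b = 0 (only active-only fires) and a = 3, b = 2 (only all-subjects fires).

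**Size if the rule were live.** With b = 0 and independent subjects, P(X ≥ r) = Σ C(6,x) pˣ(1−p)⁶⁻ˣ for x from r to 6. The gap between readings is P(X = 4) = 15p⁴(1−p)². The rates p of qualifying events on active drug are assumptions.

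| p | 5 of 6 | 4 of 6 | gap |
|---|---|---|---|
| 0.1 | 0.0001 | 0.001 | 0.001 |
| 0.3 | 0.011 | 0.070 | 0.06 |
| 0.5 | 0.109 | 0.344 | 0.23 |
| 0.8 | 0.655 | 0.901 | 0.25 |

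If each placebo subject had a 10% chance of a related qualifying event, the all-subjects figures at 0.3, 0.5 and 0.8 would be 0.024, 0.157 and 0.703.

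With 4 active subjects reviewed, active-only needs 3 of 4. Subjects with data needs 3 of 5 (one placebo) or 4 of 6 (two placebo). A denominator held at 8 needs 5, and four affected subjects give 4/8 = 50%, which does not exceed 50%. At p = 0.5, needing 3 of the 4 active subjects has probability 0.3125; needing all 4 has 0.0625.

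**Where the rule can still act.**

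1. *From 90 to 160 mg.* Section 1.2.5 reports the seven original groups complete, and Sections 1.2.5 and 1.4.3.4 describe their events as infrequent and mild. Item 2 counts only moderate or severe events, so on that description the count is 0 under every denominator.
2. *After 160 mg.* Section 1.2.5 states: "The clinical trial protocol is being amended to add the new maximum dose level of 160 mg". Sections 3.1 and 7.7 forbid exceeding the highest approved dose, so there is no further step to stop.
3. *An added group.* The cap of 72 leaves 72 − 64 = 8 subjects, one group, at a dose no higher than 160 mg. It matters only if dosed before 160 mg. The final SAP of 16 April 2021 lists exactly the eight planned doses (Table 6.1: 1) and indexes the power model k = 1 to 8 (Section 7.5.2).
4. *Dosing within group 8.* Section 3.1 requires the drug to have been safe and well tolerated in every subject of Cohorts 1 and 2 before Cohort 3 starts. That condition does not depend on any percentage.

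**Earlier gate.** Cohort 3 has 3 active subjects, so a = 4 needs at least 4 − 3 = 1 qualifying event in Cohorts 1 and 2. Unless that event came late, it would already have been weighed at the Cohort 3 gate.

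**Effect on results.** The primary endpoint is tabulated by treatment with placebo pooled across groups (SAP Sections 6.1 and 7.8.1). Item 2's denominator enters no estimate.

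**The case for a change.** The best case for a change is that a compulsory safety criterion should give one answer, and that one sentence would secure it. Judgement by the Principal Investigator and Clinical Trial Lead may halt escalation sooner, but it does not decide whether a mandatory criterion has been met. Section 3.1 also allows an individual to be dosed only while no pre-specified stopping criterion is met. If item 2 were used that way before Cohort 3 of group 8, with 3 active and 1 placebo dosed, it would need 2 of 3 active, 3 of 4 dosed, or 5 of 8 planned; four dosed subjects cannot reach the last.

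The point about wording stands: the text is open and nothing else in the documents closes it. The point about consequence largely does not. Section 3.1's individual-dosing gate refers to Section 3.3.4.1, the criteria for single subjects, whereas item 2 is framed as a limit on escalation, and the cohort gate already covers all earlier subjects. Items 2, 5 and 7 are separate rules for different events, so their different bases are not a contradiction. A single drug-related serious event, or severe related events in two subjects, would act without reference to item 2's percentage.

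**Conclusion.** No change is needed. The denominator in item 2 is undefined and the arithmetic is right: 5 against 4 in a full group, a difference of one subject. At assumed event rates of 30% to 80% the readings differ in firing probability by 0.06 to 0.25, but that describes a decision this protocol version has essentially no remaining occasion to take. At a 10% rate the difference is about 0.001.

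This rests on three things: that the protocol's summary of mild events in groups 1 to 7 is complete (the adverse-event table itself is not in the public copy); that no intermediate group was dosed before 160 mg, consistent with the SAP's list of treatments; and that the cohort gate and joint Safety Review operate as written. The point is missing detail with almost no gain from filling it. Which subjects form the denominator remains the sponsor's clinical decision, and nothing here favours either reading.

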### **3.3.5 Replacement of subjects**

If some subjects do not complete the trial, the Clinical Trial Lead together with the Trial Pharmacokineticist and the Trial Statistician are to decide, if and how many subjects will be replaced. A replacement subject will be assigned a unique trial subject number, and will be assigned to the same treatment as the subject he replaces.

## **4. TREATMENTS**

### **4.1 INVESTIGATIONAL TREATMENTS**

The investigational product has been manufactured by BI Pharma GmbH & Co. KG.

#### **4.1.1 Identity of the Investigational Medicinal Products**

The characteristics of the test product are given below:

Substance: BI 1595043

Pharmaceutical formulation: Powder for oral solution

Source: BI Pharma GmbH & Co. KG, Germany

Unit strength: 2.5 mg/mL

Posology: 1-0-0 (0.4 mL = 1 mg, 1.2 mL = 3 mg, 2.4 mL = 6 mg,  
4.8 mL = 12 mg, 10 mL = 25 mg, 20 mL = 50 mg,  
36 mL = 90 mg, 64 mL = 160 mg)

Route of administration: oral

Duration of use: Single dose

The characteristics of the reference product (placebo) are given below:

Substance: Not applicable, solvent only (Tartaric acid 5 mg/mL)

Pharmaceutical formulation: Solvent only

Source: BI Pharma GmbH & Co. KG, Germany

Unit strength: Not applicable

Posology: 1-0-0 (0.4 mL, 1.2 mL, 2.4 mL, 4.8 mL, 10 mL,  
20 mL, 36 mL, 64 mL)

Route of administration: oral

Duration of use: Single dose

#### **4.1.2 Selection of doses in the trial**

The doses selected for this trial cover the subtherapeutic as well as the estimated therapeutic range and include a safety margin (see Section [1.2](#)).

#### **4.1.3 Method of assigning subjects to treatment groups**

Prior to the screening visit, subjects will be contacted in writing and informed about the planned visit dates. The subjects willing to participate will be recruited to dose groups (3 cohorts per dose group) according to their temporal availability. As soon as enough

Proprietary confidential information © 2021 Boehringer Ingelheim International GmbH or one or more of its affiliated companies

subjects are allocated to 1 of the 21 dose cohorts, the following subjects will be allocated to one of the other dose cohorts. Therefore, the allocation of subjects to dose cohorts is not influenced by trial personnel, but only by the subjects' temporal availability. Because the trial includes healthy subjects from a homogenous population, relevant imbalances between the dose groups are not expected.

Subjects will be assigned to treatments (active treatment or placebo) prior to the first administration of trial medication. In Cohorts 3 of each dose group, subjects will be randomly assigned to treatments, while treatments in Cohort 1 and Cohort 2 will be assigned in a fixed order for safety reasons, as described in Section [3.1](#).

For the purpose of random assignment, the randomisation list will be provided to the trial site in advance. Numbers of the randomization list will be allocated to subjects by the method 'first come - first served' at the time of registration. Subjects are then assigned to treatment according to the randomisation list. Once a subject number has been assigned, it cannot be reassigned to any other subject.

The randomisation procedure is described in Section [7.6](#).

#### **4.1.4 Drug assignment and administration of doses for each subject**

The treatments to be evaluated are outlined in Table [4.1.4: 1](#) below. The dose volume for placebo corresponds to the dose volume of the corresponding dose level.

Table 4.1.4: 1 BI 1595043 and placebo treatments, oral administration

Dose group	Substance	Pharmaceutical form	Unit strength	Dose volume per administration	Total daily dose
1	BI 1595043	oral solution	2.5 mg/mL	0.4 mL q.d.	1 mg
2	BI 1595043	oral solution	2.5 mg/mL	1.2 mL q.d.	3 mg
3	BI 1595043	oral solution	2.5 mg/mL	2.4 mL q.d.	6 mg
4	BI 1595043	oral solution	2.5 mg/mL	4.8 mL q.d.	12 mg
5	BI 1595043	oral solution	2.5 mg/mL	10 mL q.d.	25 mg
6	BI 1595043	oral solution	2.5 mg/mL	20 mL q.d.	50 mg
7	BI 1595043	oral solution	2.5 mg/mL	36 mL q.d.	90 mg
8	BI 1595043	oral solution	2.5 mg/mL	64 mL q.d.	160 mg
1-8	Placebo*	oral solution (solvent only)	--	identical to active treatment	--

\* Subjects receiving placebo are equally distributed across dose groups

The oral solutions for dosing (active treatment and placebo) will be prepared by pharmacists or qualified pharmacy staff members or qualified medical study personnel at the trial site under the responsibility of the investigator according to the instructions provided in Appendix [10.1](#).

Administration of trial medication will be performed after subjects have fasted overnight; fasting is to start no later than 10 h before the scheduled dosing. The investigator (or

Proprietary confidential information © 2021 Boehringer Ingelheim International GmbH or one or more of its affiliated companies

authorised designee) will administer the trial medication as an oral dose together with about 240 mL of water to subjects who are in a sitting or standing position. For drug administration, the so-called four-eye principle (two-person rule) should be applied. For this, one authorised employee of the trial site should witness the preparation of trial medication and its administration to subjects.

Subjects will be kept under close medical surveillance until 48 h after drug administration. During the first 2 h after drug administration, subjects are not allowed to lie down (i.e. no declination of the upper body of more than 45 degrees from upright posture except for medical examination) or to sleep.

